13.3. Complaints

During the study, the investigator will be responsible for reporting all complaints. A complaint is defined as any written, electronic or oral communication that alleges deficiencies related to the identity, quality, durability, reliability, safety, effectiveness or performance of a device after it is released for distribution.

If the complaint does not involve a reportable AE as defined in this protocol, the investigator must notify the Post Market Surveillance Department by submitting the information on the device via email to [contact] or by phone toll free: [name] as soon as possible after becoming aware of the complaint. This information will not be collected on a CRF for the study.

If the complaint involves a reportable AE as defined in this protocol, the investigator must complete an AE CRF, including the information on the complaint and submit to the Sponsor as soon as possible.

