16.1. Adverse events

To comply with worldwide standards and guidelines on clinical study adverse event reporting, the Sponsor has adopted uniform and worldwide applicable standard definitions and reporting timelines to be used and adhered to by the investigators.

Safety surveillance within this study and the safety reporting, both performed by the investigator, starts as soon as the subject's MRI Settings have been programmed during the MRI visit.

Adverse events will be monitored until they are adequately resolved, or the subject has ended his/her participation in the study, whichever comes first. The status of the subject's condition should be documented at each visit.

Reportable events shall be submitted to the Sponsor. The Sponsor will ensure that all applicable events and device deficiencies are reported to the relevant authorities as per regulations. The sites should notify the Sponsor of reportable adverse events by creating and saving the applicable CRF within the electronic data capture (EDC) system.

Additional information may be requested by the Sponsor to support the reporting of AEs to regulatory authorities. The investigator must notify the IRB/EC, if appropriate, in accordance with national and local laws and regulations, of the AEs reported to the Sponsor.

All study related adverse events will be reported as per applicable regulatory requirements. The Sponsor will also notify all the other medical institutions conducting the clinical study and Ethics committees of the occurrence of SAEs.

Unchanged, chronic, non-worsening or pre-existing conditions are not AEs and should not be reported.

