16.1.1. Criteria and Guidelines for Non-Reportable Events

Except as otherwise noted in the CIP, the following events are not reportable to the sponsor:

- Events that occur prior to the MRI settings have been programmed at the MRI study visit.

NOTE: Since all products in the study are market released and will be used per the approved indication prior to programming MRI settings, the Principal investigator will be responsible for reporting these events as device complaints as they would for any market approved product (See Section 13.3).

- Events not related to the procedure remove, replace or reposition the study lead or ICD/ CRT-D.
- Unavoidable events, as listed in **Table 11** that resolve within the timeframes specified.

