3.5 Descriptive Endpoints or Additional Data

Following Descriptive Endpoints will be reported using only summary statistics and no hypothesis tests will be performed.

- 1) Demographics: gender, age, ethnicity, race, cardiac disease history, arrhythmia history, indication for ICD/CRT-D implant, history of smoking, etc. Refer to Section 3.1 for the detail.
- 2) Device electrical measurements: device electrical measurements at the MRI Scan Visit (pre- and post-scan) and at the 1-Month Post Scan Visit will be summarized based on Analysis Cohort subjects who undergo the 1-month post-MRI scan testing, and with evaluable device data available for analysis to be performed.
- 3) ADE, SADE, USADE: Refer to Section 3.2 for the detail.
- 4) Mortality: The number of subjects who die and the primary cause of death will be presented based on the CEC adjudicated data.
- 5) Non-study MRI scan data: The number, type, available adverse event(s), and key electrical measurements will be summarized for non-study MRI scans performed.
- 6) Summarize number of subjects that returned to usual programming after the MRI scan and number of subjects, if any, experiencing delays in reprogramming: Data will be summarized descriptively based on available information from MRI Scan form. A subject with 'Yes' to question of 'Were the MRI settings disabled after MRI scan' in MRI Scan form is considered as 'returned to usual programming after the MRI scan'.

In addition, the adverse events and mortality that are reported prior to the completion of the study pre-MRI scan visit on the All Consented subjects will be summarized separately using descriptive statistics. Listings of the adverse events and mortality with an event description will be provided as appropriate.

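### SAP 3.5 summarises pre-MRI adverse events over all consented subjects, but the CIP lets only a selective subset of them be recorded, so any percentage would understate incidence

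*Combined protocol and SAP*

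**What the plan says.** After its six numbered descriptive endpoints, SAP 3.5 adds that adverse events and mortality reported "prior to the completion of the study pre-MRI scan visit on the All Consented subjects will be summarized separately", by descriptive statistics and with listings as appropriate. SAP 3.0 sends everything in that chapter to the methods of SAP 2.2. For categorical data, SAP 2.2.2 specifies counts with percentages or rates and allows exact 95% intervals.

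CIP 16.1.1 opens its list of exclusions with "Except as otherwise noted in the CIP, the following events are not reportable to the sponsor". The first item is "Events that occur prior to the MRI settings have been programmed at the MRI study visit". A note there makes the principal investigator "responsible for reporting these events as device complaints as they would for any market approved product", and points to CIP 13.3. That section says of a complaint without a reportable adverse event: "This information will not be collected on a CRF for the study".

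**The concern.** The SAP plans a safety summary for a period in which the CIP tells sites not to report adverse events to the sponsor. The denominator is everyone who consented. The numerator is whatever reaches the database by a few side routes.

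If the default output is produced, the report will show an adverse event percentage for the implant and stabilisation period that is low largely because events were not asked for. The report supports a labelling submission to the NMPA. A reader there would take a percentage over all consented subjects as an incidence, and nothing in SAP 3.5 warns that reporting was switched off for this period.

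**Working it through.** The plan states no figure for this summary, so there is nothing to reproduce. The check is a comparison of the two documents, followed by arithmetic for scale.

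**1. Is a pre-MRI adverse event reportable?** As a rule, no.
- CIP 16.1.1 excludes it.
- CIP 16.1 starts surveillance once the subject's "MRI Settings have been programmed during the MRI visit", and CIP 8.3.2 agrees.
- In CIP 16.1.2, SAE reporting and the reporting of ADEs and SADEs unrelated to the scan are confined to the time after programming.
- CIP Table 2 ticks adverse event collection at three visits, consistent with MRI Scan, 1-month and Unscheduled, and at none before.
- CIP 8.1.3 limits CEC adjudication to events after programming.

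**2. Does the complaint route bring it back?** Normally not. CIP 13.3 has two branches: an AE CRF if the complaint involves a reportable adverse event, and no CRF otherwise. Because 16.1.1 makes the event non-reportable, the second branch applies. A complaint must also be "any written, electronic or oral communication that alleges deficiencies related to the identity, quality, durability, reliability, safety, effectiveness or performance of a device", so an adverse event with no alleged device deficiency has no route at all.

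**3. What can still be recorded before the scan?**
- *System revisions.* CIP Table 4 covers revisions at any time after implant and asks for an adverse event evaluation, with an AE CRF where applicable. The opening exception in 16.1.1 leaves room for this.
- *Deaths.* CIP 16.1.3 requires them on the AE, Withdrawal and Product Out of Service CRFs and states no start date. Pre-scan deaths are therefore captured, although the CEC does not adjudicate them.

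The summary would therefore hold a selective subset. It need not be empty.

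**4. How long is the period?** Windows from CIP Tables 2 and 4, with no revision:
- Consent to implant 0 to 7 days; implant to baseline 45 to 52; baseline to scan 0 to 14.
- Before the scan: 0 + 45 + 0 = 45 days at the shortest, 7 + 52 + 14 = 73 at the longest.
- After the scan: 30 to 44 days.
- Pre-scan share: 45/(45+30) = 60%; 45/(45+44) = 51%; 73/(73+30) = 71%; 73/(73+44) = 62%.

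CIP 8.4 counts the 45 days from discharge, and 8.4.4.3 gives 45 days only as a minimum. Either would lengthen the period.

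**5. What might be missing?** The documents give no pre-scan event rate and no capture fraction, so both are assumed here. Let q be the per-subject risk of a pre-scan event and c the fraction of affected subjects recorded. With 60 subjects, the expected number affected is 60q, the number missing is 60q(1 − c), and the displayed percentage averages q × c.

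| Assumed q | Expected affected (60q) | Chance of at least one, 1 − (1 − q)^60 | Missing, c = 0 | Missing, c = 0.25 | Missing, c = 0.5 |
|---|---|---|---|---|---|
| 2% | 1.2 | 70% | 1.2 | 0.9 | 0.6 |
| 5% | 3 | 95% | 3 | 2.25 | 1.5 |
| 10% | 6 | 99.8% | 6 | 4.5 | 3 |

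For example, at q = 5% and c = 0.25 the table would show 1.25% on average. If nothing were recorded, 0/60 would carry an exact two-sided 95% upper limit of 1 − 0.025^(1/60) = 6.0%. That interval covers sampling error only and says nothing about events that were never collected.

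**The case against.** The strongest defence is that SAP 3.5 speaks of events that are reported. It promises a description of what is in the database, keeps it apart from the numbered endpoints and adds listings. It names no percentage for this summary, and SAP 2.2.2 makes confidence intervals optional. All of that is true. But descriptive statistics for categorical data under SAP 2.2.2 are counts with percentages, and SAP 3.5 makes no exception. Limiting the numerator to reported events leaves the denominator at all consented subjects.

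A second defence is that little depends on it. The devices are market-approved, the scan is the investigational element, the study's safety window opens at MRI programming, and the study has no hypothesis test or success criterion. This stands as a limit on the importance of the point.

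Third, some material cannot be seen. SAP 2.1 is redacted, so the definition of the All Consented population is not visible, and the CRFs are under separate cover. This stands as a reservation about exactly what reaches the database.

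A reader might go further and infer two things that the documents do not support:
- *That the pre-scan rate will come out near zero, because no such event can reach a CRF.* The revision row of Table 4 and the death rule are documented routes.
- *That the summary hides why consented subjects never reach the scan.* CIP 8.4.5 and Table 8 require withdrawal or screen failure forms, CIP 14.6 requires the reason for discontinuation to be notified, SAP 3.3 summarises early termination reasons, and CIP 20 puts disposition and withdrawals in the study report.

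**Conclusion.** The conflict holds. Under both documents as written, the pre-MRI adverse event summary would be drawn from a selective subset, and a percentage over all consented subjects would be biased low. The size of the bias cannot be derived from the documents; the table of missing events rests on assumed risks and capture fractions and only shows scale. What does follow from the visit windows is that the period covers about half to seven tenths of a subject's time in the study.

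The mortality part of the summary is not affected in the same way, because deaths are reportable throughout. No primary endpoint is touched. The change is still worth making, because the report goes to a regulator and the correction needs only SAP wording.

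There is a smaller mismatch of cut-points. The SAP ends the period at completion of the pre-MRI visit, the CIP at programming of MRI settings. CIP Table 7 foresees subjects who attend the pre-scan visit and are never programmed, so the two are not always the same.

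**What to change.** In SAP 3.5:
- Keep the pre-MRI mortality summary on all consented subjects.
- Present other pre-MRI adverse events, including those at system revisions, as counts and a listing, with no percentage, rate or confidence interval. Label them *not systematically collected before MRI-settings programming (CIP 16.1.1)*.
- End the period at programming of MRI settings, as the CIP does.

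This costs SAP wording only. Deleting the summary altogether would be worse, since it would drop events that were reported.

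If the sponsor wants a pre-scan incidence, amend CIP 16.1.1 so that pre-scan ADEs and SADEs are recorded on the AE CRF, and bring CIP 8.3.2, 16.1, 16.1.2 and Table 2 into line. That takes a protocol amendment and some added data entry at sites.

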4.0 DOCUMENTATION AND OTHER CONSIDERATIONS

All analyses will be performed using SAS® for Windows, version 9.3 or higher.

5.0 ACRONYMS AND ABBREVIATIONS

Acronym or Abbreviation	Complete Phrase or Definition
CEC	Clinical Events Committee
CIP	Clinical Investigation Plan
CRF	Case Report Form

Statistical Analysis Plan

Acronym or Abbreviation	Complete Phrase or Definition
SAE	Serious Adverse Event
ADE	Adverse Device Effect
SADE	Serious Adverse Device Effect
USADE	Unanticipated Serious Adverse Device Effect
SAP	Statistical Analysis Plan
NMPA	China National Medical Products Administration
MRI	Magnetic Resonance Imaging
ICD	Implantable Cardiac Defibrillator
CRT-D	Cardiac Resynchronization Therapy Defibrillator

